### **Specific Aims**

**Aim 1.** To compare the incidence of adverse events in patients following a SDD protocol for minimally invasive sacrocolpopexy compared to those patients discharged on POD 1.

We hypothesize that there is no difference in the incidence of adverse events between SDD compared to discharge on POD 1 after minimally invasive sacrocolpopexy. Using the *Epic* electronic medical record (**EMR**), we will evaluate 1) the number of unscheduled office visits, patient-initiated calls for a surgery-related complication, emergency department visits, and readmissions/reoperations of patients who had a SDD protocol and 2) the severity of any adverse events using the Clavien Dindo Scale. We will utilize patient phone calls to inquire about any of the aforementioned events outside of our institution. We will compare incidence of postoperative adverse events between patients undergoing SDD versus a historical control group who were discharged on POD 1.

**Aim 2.** To compare the total procedure-related costs associated with SDD compared to discharge on POD 1 for minimally invasive sacrocolpopexy.

We hypothesize that the total costs associated with SDD following minimally invasive sacrocolpopexy is less than the same procedure with discharge on POD 1. We will utilize data from the billing function of *Epic* EMR to compare total procedure-related costs for each approach to minimally invasive sacrocolpopexy.

**Aim 3.** To determine patient satisfaction with SDD after minimally invasive sacrocolpopexy.

We hypothesize that patients will be satisfied with SDD after minimally invasive sacrocolpopexy. We plan to address this aim using a series of validated measures.

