#### **Secondary outcomes:**

- Patient-initiated phone calls for a surgery-related complication

- Unscheduled office visits, including voiding trials
- Emergency department visits
- Cost of surgery/post-operative hospitalization
- Quality of Recovery (QoR-15), a validated questionnaire created to measure a patient's early post-operative status
- Visual analog scale (VAS) pain scores
- Minimally invasive sacrocolpopexy survey

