## **2. Study Population and Subject Identification**

### **Eligibility Criteria**

Patients of the Center of Urogynecology and Pelvic Reconstructive Surgery in the Department of Ob/Gyn and Women's Health Institute or the Female Urology division in the Department of Urology at the Cleveland Clinic scheduled to undergo a minimally invasive (robotic-assisted or laparoscopic) sacrocolpopexy for pelvic organ prolapse with a board-certified female pelvic medicine and reconstructive surgery specialist will be approached for participation in this study.

Additional surgical procedures may include: hysterectomy (either total or supracervical), trachelectomy, anterior and/or posterior colporrhaphy, enterocele repair, minimally invasive Burch colposuspension or paravaginal defect repair, vaginal mesh removal or revision, vaginal graft placement, midurethral sling, or perineal rectal prolapse repair (Delorme or Altemeier).

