### **3. Data Collection**

The EMR will be reviewed to collect preoperative, intraoperative, and POD 0 data points. We will use the following method to identify the occurrence of a procedure-related adverse event: The EMR will be reviewed for patient phone calls for a procedure-related complication, unscheduled office visits, emergency department visits, hospital readmissions or reoperations within 30 days, and adverse events occurring up to 6 weeks post-operatively. The adverse events of interest will include the following:

- Wound infection
- Hematoma
- Transfusion
- Pelvic abscess
- Osteomyelitis
- Venous thromboembolism (deep vein thrombosis or pulmonary embolism)
- Delayed bowel or urinary tract injury
- Bowel obstruction or ileus
- Cardiac or pulmonary complication
- Neurologic injury

We will also employ an approach that will allow us to capture events that may have been handled outside of the CCHS or in institutions that do not utilize *Epic*. To capture these data points if they exist, we will contact participants by telephone on POD 1 (within 24 hours of surgical completion time) to determine if they received any care from a facility outside of the CCHS and then again at the post-operative follow up visit, which generally occurs at 6 weeks. We will then use these data with the Clavien Dindo Scale to determine the severity of the adverse event, with a grade 3 or higher considered to be a serious adverse event, and we will compare this proportion to the reference proportion of 26.3%. A proportion of patients with grade 3 or higher less than 45.1% will be considered non-inferior to the reference.

As part of the effort to characterize the patient population, we will extract data regarding total procedure-related costs using the EMR. We will assess satisfaction using the quality of recovery questionnaire, visual analog scores for postoperative pain, and a patient satisfaction survey described by Fountain et al at the postoperative visit, which uses a Press Ganey scale for responses (See Appendix A). Please see data collection sheet for a comprehensive list of planned data points.

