### **4. Statistical Plan**

*Statistical analysis:* Categorical variables will be presented as n/N (%) with 95% confidence intervals. Continuous variables will be presented as mean +/-SD or median [range]. A Pearson's chi-square test or Fisher exact test will be used for frequencies and proportions of categorical values and t test or the non-parametric Wilcoxon rank sum test for mean values of continuously measured variables. P values  $\leq 0.05$  will be considered statistically significant and we will use SAS (version 9.4, The SAS Institute, Cary NC) as our statistical package to perform these analyses. The primary investigator will perform the statistical analysis with assistance from the WHI statistician.

We will use data from a historical control group discharged on POD 1 after minimally invasive sacrocolpopexy to examine Aim 1 and Aim 2. This is a cohort of 60 women matching our eligibility criteria from a prospective randomized trial of two different types of lightweight polypropylene mesh (IRB #14-354). This study completed recruitment 2017. It consists of a group of women who underwent minimally invasive sacrocolpopexy using the same surgical approaches, at the same institutions (main campus, Fairview and Hillcrest), and performed by the same surgeons as our study. The primary difference is that participants in that study and the cohort proposed here is that all participants were discharged home on POD 1. We will utilize this cohort to compare the incidence and severity of procedure-related adverse events and costs between SDD and POD 1. Comparisons on outcome measures will be done using either an ANOVA analysis or a student's t test for parametric continuous outcomes, a Kruskal-Wallis or Mann Whitney U test for non-parametric outcomes and a Chi-square test for all categorical outcomes. Logistic regression will be performed to control for confounding variables.

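### Aim 2 compares one total cost that includes the operation with a historical cohort, without a suitable adjustment, so an operating-cost difference can hide or imitate the saving from one fewer night.

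*Combined protocol and SAP*

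**What the plan says.** Specific Aims, Aim 2 gives a directional hypothesis on the total: "We hypothesize that the total costs associated with SDD following minimally invasive sacrocolpopexy is less than the same procedure" with POD 1 discharge. Billing data will be used to "compare total procedure-related costs for each approach to minimally invasive sacrocolpopexy". The list of secondary outcomes has one cost item, "Cost of surgery/post-operative hospitalization", so the operation is part of the figure. Section 3 (Data Collection) again names only the total: "we will extract data regarding total procedure-related costs using the EMR". No section plans a separate analysis of operating and post-operative cost.

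Section 4 (Statistical Plan) describes the comparator: "This is a cohort of 60 women matching our eligibility criteria from a prospective randomized trial of two different types of lightweight polypropylene mesh". It adds: "This study completed recruitment 2017". Continuous outcomes are to be compared by t test or ANOVA, or by a rank test. Logistic regression is the only method named for confounding.

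The same section says that approaches, institutions and surgeons are the same in both cohorts. Section 6 (Research Environment), however, says that two staff who joined in 2017 also perform the operation and will recruit. The Eligibility Criteria allow a robotic or laparoscopic route and a long list of concomitant surgery: "Additional surgical procedures may include: hysterectomy (either total or supracervical), trachelectomy, anterior and/or posterior colporrhaphy", and more. Beyond the statement that the controls match the eligibility criteria, no balancing on route or concomitant procedures is described.

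**The concern.** In a randomized comparison, including the operation in the total would mainly add noise. Here the cohorts are not randomized, so a difference in mean operating cost also adds bias. Discharge day does not change whether the operation was robotic, which procedures accompanied it or who performed it. If the mix of these differs between the cohorts, the difference in totals contains that contribution in full, and no planned step removes it or shows it.

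Two errors are possible. A real saving from one fewer night could be lost in operating-cost variation or cancelled by a costlier case mix in the SDD cohort. Conversely, a cheaper case mix could be reported as a saving from SDD.

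**Working it through.** **The plan's own figures.** Aim 2 has no mean, SD, target difference or power, so there is no figure to reproduce. The only sample-size calculation (section 4) concerns the primary outcome. It does reproduce: with n = 45, reference 26.3% and an assumed one-sided 5% level, the exact test rejects at 18 or more events and has 80% power at 45.15%, against the stated 45.1%. It says nothing about cost.

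**Inputs.** From the documents: 45 SDD patients, 60 controls, significance at 0.05. Assumed: a two-sided test (none is stated for cost), and all cost sizes and SDs below.

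**Step 1: precision.** The standard-error factor is sqrt(1/45 + 1/60) = 0.197, and the t quantile on 103 df is 1.98. Let the saving be 1 unit, with operating and post-operative cost independent. Then SD(total) = sqrt(SD_op² + SD_post²), and the 95% half-width is 1.98 × 0.197 × SD.

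With SD_post = 1:

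| SD_op | SD of total | 95% half-width | Power on total |
|---|---|---|---|
| 0.5 | 1.12 | 0.44 | 99% |
| 1 | 1.41 | 0.55 | 94% |
| 2 | 2.24 | 0.87 | 61% |
| 3 | 3.16 | 1.24 | 36% |
| 4 | 4.12 | 1.61 | 23% |

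The post-operative part alone (SD 1) has a half-width of 0.39 and power above 99%.

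**Step 2: the same check with a more variable post-operative part.** This part includes later care, so its SD may be well above 1. With SD_op = 2:

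| SD_post | Power on post-operative part | Power on total |
|---|---|---|
| 1 | over 99% | 61% |
| 2 | 71% | 43% |
| 3 | 39% | 29% |

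Some SDD patients will stay overnight under the disposition rule in Day of Surgery. At the 83.3% SDD rate of the preliminary study cited in Background & Significance, a saving of 1 unit averages 0.833. With SD_post = 2, power on the post-operative part is then 55%.

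**Step 3: bias.** Apparent saving = true saving − (mean operating cost in SDD − mean operating cost in controls). An operating-cost shift equal to the saving doubles or erases it at any sample size.

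To give this a scale, set mean operating cost to 1, assume the night costs 0.10, and take the SD of the total as 0.15 or 0.25. The chance of a significant result favouring SDD is 1 − Φ(1.96 − apparent saving / (0.197 × SD)):

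| True saving | SDD operating cost | SD 0.15 | SD 0.25 |
|---|---|---|---|
| 10% | equal | 92% | 53% |
| 10% | 5% higher | 39% | 17% |
| 10% | 10% higher | 2.5% | 2.5% |
| none | 5% lower | 39% | 17% |
| none | 10% lower | 92% | 53% |

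**Step 4: could shifts of this size arise?** The documents do not say. If robotic surgery adds 10% to 30% to operating cost and the robotic share differs by 10 to 30 percentage points, the mean shifts by 0.10 × 0.10 = 1% up to 0.30 × 0.30 = 9%.

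**The case against.** **Only cost after the operating room can respond to SDD.** A reader might infer this, but the documents do not support it. The intervention is a planned pathway, and the hypothesis in Background & Significance is about an ERAS protocol that uses SDD. Preoperative Visit and Day of Surgery place the video, the prescriptions, the preemptive analgesics and the intraoperative antiemetics before or during surgery. Those costs belong to the pathway. What stands is narrower: discharge day does not change route, concomitant procedures or surgeon.

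**The total is the wrong endpoint.** This does not follow either. Total cost is a legitimate hospital or payer endpoint and is the question Aim 2 asks. Replacing it would change the question. Reporting components beside it does not.

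**The controls are stated to be comparable.** Section 4 does say so, and that deserves weight. But section 6 weakens the claim about surgeons, and using the same range of approaches does not mean using them in the same proportions. That the controls came from a trial of "two different types of lightweight polypropylene mesh" should not be pressed: nothing says that mesh type or price differs between the cohorts.

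**Components may already be planned.** The slash in the outcome item could mean two items, and the data collection sheet cited in section 3 is not in the text available and may list cost categories. Even so, no component analysis is specified and the hypothesis is on the total.

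**Splitting is not a cure.** This is correct. Concomitant procedures and calendar time can also affect recovery cost and later care. The split removes the direct operating-cost contribution and no more.

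**Conclusion.** The concern holds as a weakness of analysis and attribution in a secondary aim for which no power is claimed. It is not an error in any stated figure. As written, Aim 2 cannot tell a saving from one fewer night apart from a difference in the operations performed, and the plan names no adjustment that fits a continuous cost.

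The direction of any bias is unknown, and so is its size. The power figures rest wholly on assumed SDs, and a reader should not conclude that the total is shown to be underpowered or that the post-operative part is sure to have over 99% power. With a saving of 1 unit, power on the total runs from 99% to 23% across operating-cost SDs of 0.5 to 4 (post-operative SD 1). Power on the post-operative part falls from over 99% to 39% as its SD goes from 1 to 3. The bias argument needs none of these values. It needs only a difference in mean operating cost between the cohorts, which the plan neither excludes nor checks.

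The change is a cheap and worthwhile improvement, not a condition for the study to proceed.

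**What to change.** In Aim 2, the secondary outcomes and section 3, keep total cost as the stated endpoint. Before any cost data are examined, prespecify the following:

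- A split into (a) operating-room cost and (b) post-operating-room cost: PACU, stay and later care.
- A fixed rule that assigns pathway-specific preoperative and intraoperative items (ERAS drugs, video, prescriptions) to the SDD pathway cost.
- The mean difference with a 95% interval for each component and for the total.
- Component (b) plus the pathway items as the key estimate for attributing a saving to SDD, and component (a) as the check on cohort comparability. A difference in the total that arises in (a) is not attributed to SDD.

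The report should say that the split leaves some historical-control confounding in (b).

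The cost is SAP wording, extraction of billing lines by cost centre in both cohorts, and an allocation rule for shared items, which will be partly arbitrary. No patients or visits are added.

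### Aim 2 claims total procedure-related cost but draws it only from the institution's own billing, so care given elsewhere counts as an event at zero cost

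*Combined protocol and SAP*

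**What the plan says.** The aim is broad. Specific Aims, Aim 2, reads "To compare the total procedure-related costs associated with SDD compared to discharge on POD 1".

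The source is narrow. Aim 2 continues "We will utilize data from the billing function of" the Epic record, and section 3 (Data Collection) says "we will extract data regarding total procedure-related costs using the EMR". No other cost source is named.

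For adverse events the plan goes further. Aim 1 says "We will utilize patient phone calls to inquire about any of the aforementioned events outside of our institution". Section 3 describes an approach to "capture events that may have been handled outside of the CCHS or in institutions that do not utilize" Epic: a telephone contact on POD 1 and a further question at the visit at about 6 weeks, each "to determine if they received any care from a facility outside of the CCHS". Neither contact is described as collecting a cost.

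The Secondary outcomes list defines the endpoint differently, as "Cost of surgery/post-operative hospitalization". No time window for cost is stated anywhere.

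The comparator is historical. Section 4 (Statistical Plan) says "We will use data from a historical control group discharged on POD 1 after minimally invasive sacrocolpopexy to examine Aim 1 and Aim 2". It consists of 60 women from an earlier randomized mesh trial.

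**The concern.** The plan applies two standards of completeness to the same record. For Aim 1 it allows that the institution's record may miss care and adds patient contacts to find it. For Aim 2 it uses that record alone and calls the result a total. Nothing provides for outside bills, insurer claims or a standard unit cost.

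The gap is not fully symmetric. Every control was still in hospital on the first night, so a problem that night was handled and billed in-house. An SDD woman who has gone home could, that same night, be treated at a facility that sends no bill to this institution. Missing that cost lowers the SDD mean and moves the comparison towards the Aim 2 hypothesis. The background section says the study should supply the data needed for wide adoption of SDD and names lower resource use as an expected benefit, so a claim about total cost would carry weight.

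**Working it through.** **Figures available.** The plan has no cost figure to reproduce. Its only design calculation concerns adverse events (45 evaluable patients, 47 with 3% dropout: 45 / 0.97 = 46.4, rounded up). Only the 45 is used below.

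**Where a missed cost can arise**

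| Care received | SDD woman | POD 1 control |
|---|---|---|
| First night, at this institution | billed | billed (inpatient) |
| First night, elsewhere | reported on POD 1, cost zero | essentially cannot occur |
| Later, at this institution | billed | billed |
| Later, elsewhere | reported at about 6 weeks, cost zero | cost zero; the documents do not say how outside care was ascertained |

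Only the second row differs by design. The fourth distorts the comparison only if later outside care is more frequent or more costly in one group, and the documents do not show that.

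**Size relative to the billed saving.** Let A be the mean saving seen in billing. Suppose k of 45 SDD women each have one unbilled outside episode costing c × A, and controls have none. The corrected saving is A × (1 − k × c / 45).

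- With c = 10 (assumed): k = 1 removes 10/45 = 22% of the billed saving, k = 2 removes 20/45 = 44%, and k = 3 removes 30/45 = 67%.
- The saving falls to zero at c = 45 / k, that is 45, 22.5 and 15 for k = 1, 2 and 3.

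**Size in money, on assumed unit costs.** Take 2,000 for an emergency visit and 20,000 for a readmission. Both are assumptions, as is a saved night worth 1,000 to 2,000.

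- Low end, one emergency visit: 1 × 2,000 / 45 = 44 per woman.
- High end, three readmissions: 3 × 20,000 / 45 = 1,333 per woman.

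**Size at the rates the documents cite.** The background section gives these for related procedures. Suppose every such event went outside and cost the assumed 20,000, with no offset in controls.

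| Cited rate | Mean cost missed per SDD woman | Chance of at least one in 45 |
|---|---|---|
| 5/1071 = 0.47%, readmission or emergency evaluation within 30 days, vaginal hysterectomy | 0.0047 × 20,000 = about 93 | 1 − 0.9953^45 = 19% |
| 0.6%, readmission within 48 hours, myomectomy | 0.006 × 20,000 = 120 | 1 − 0.994^45 = 24% |
| 1.4%, readmission over 3 months, myomectomy | 0.014 × 20,000 = 280 | 1 − 0.986^45 = 47% |

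The 48-hour rate is closest to the first-night mechanism. Its 120 is 6% to 12% of the assumed saved night. The longer-window figures would be partly offset by the same loss in controls.

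**The case against.** The strongest reply is that the Secondary outcomes list confines the endpoint to surgery and the post-operative stay. On that definition outside care is out of scope and institutional billing is a proper source. This is a fair reading of that list, but Aim 2 and section 3 both use the total-cost wording. What stands is that the sections disagree and must be reconciled.

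A reader might infer that the cost of problems is lost from the SDD group only. The documents do not support that. Controls also went home, on POD 1, and any outside care afterwards is equally absent from billing. The asymmetry is confined to the first night. Even there the plan has safeguards: overnight observation for women who do not meet discharge criteria, contact instructions, calls on POD 0 (unless discharge is late) and POD 1, and a caretaker for 24 hours. These make unbilled first-night care less likely without excluding it.

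A reader might also take the bias to be most of the saving. The 1,333 figure needs three outside readmissions in 45 women (6.7%), nearly five times the 1.4% cited over 3 months. The background section also reports no difference in emergency visits or readmissions between 80 SDD and 192 later-discharge robotic sacrocolpopexies. This part of the objection stands: the effect may be small.

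Nor does the plan predict outside care. It provides for it in case it occurs. And it cannot be said that controls were questioned less thoroughly, because the documents are silent on that.

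**Conclusion.** The point holds in a limited form. As written, Aim 2 can support a statement about cost to the institution but not about total procedure-related cost, because care found through the plan's own outside-care questions carries no cost. The one difference built into the design, the first night, can only favour SDD.

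The size cannot be determined from the documents. On assumed unit costs and counts it runs from 44 to 1,333 per SDD woman. At the cited rates of about 0.5% to 1.4% it is about 93 to 280, even if every event went outside at the assumed 20,000 and controls offset nothing. Those rates come from other procedures, so they are a guide and not a bound. With 45 women, a single expensive episode could still move the mean visibly.

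Cost is a secondary outcome, and the primary safety conclusion is unaffected. The change is worth making because it is cheap and settles what Aim 2 may claim.

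**What to change.** 1. Reconcile Aim 2 and section 3 with the Secondary outcomes list, and state one cost scope and one time window.
2. Keep the billing-based comparison and describe it as institutional cost.
3. Add a sensitivity analysis. For each outside contact reported on POD 1 or at the 6-week visit, record the type of service and assign the institution's own mean cost for it (emergency visit, readmission, reoperation). Do the same for controls wherever the earlier trial recorded outside care. Where it did not, label the analysis as conservative against SDD.
4. Claim a saving in total cost only if the sensitivity analysis agrees with the billing comparison. Otherwise limit the conclusion to institutional cost, which the billing comparison can support on its own.

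The cost is a short unit-cost list, one extra analysis and a check of what the earlier trial recorded. No new patient contact is needed. The reported saving may be somewhat smaller.
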